Clinical and Radiographic Evaluation of MTA versus Biodentine as Pulpotomy Agents in Immature First Permanent Molars: A Randomized Clinical Trial

Protocol submitted to the Faculty of Dentistry, Cairo University
by
[name]
Associate Professor of Pediatric Dentistry

Faculty of Dentistry
Cairo University
18 Jan 2017

I. Administrative information:

1. Title:

Clinical and Radiographic Evaluation of MTA versus Biodentine as Pulpotomy Agents in Immature First Permanent Molars: A Randomized Clinical Trial

2. Protocol Registration:

To be registered on Clinicaltrial.gov

3. Protocol version:

Final version.

4. Funding:

This trial is self-funded.

5. Roles and responsibilities:

1. **[name] ([name])** Associate Professor of Pediatric Dentistry, Cairo University. Responsible for the clinical part of study, and Data monitoring.
2. **[name] ([name])** Professor of Pediatric Dentistry, National University of Singapore, responsible for the writing revision and proof reading.
3. **[name] ([name])** Associate Professor of Pediatric Dentistry, Misr University for sciences and technology. Responsible for the clinical evaluation of the cases at the evaluation intervals

II. Introduction

6-background and rationale:

Description of research question:

P: children with cariously exposed immature mandibular first permanent molars

I: Pulpotomy using Biodentine

C: MTA pulpotomy

O:

	Outcome	Tool/Device	Unit
Primary Outcome	spontaneous pain, sensitivity to percussion/palpation)	Pain questionnaire	Binary
	Swelling or sinus tract	Visual examination by the third author	Binary
	Mobility	Back of the mirror	Binary
Secondary outcome	Stage of root development	Standardized periapical	3 stages
	Crown: Root ratio	Standardized periapical	2:1 ≥2:1
	Apex	Standardized periapical	Blunder apex, partially open, constricted
	Presence of radiolucency	Standardized periapical	Binary

S: Randomized clinical trial

T: 18 months (Baseline, 6, 12 and 18 months)

Research question: is Biodentine used as pulpotomy material in cariously exposed immature mandibular first permanent molars more successful clinically and radiographically than MTA pulpotomy?

Justification for undertaking the trial:

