Biodentine new bioactive calcium silicate-based cement has been recently launched in the dental market as a 'dentin substitute'. This new biologically active material facilitates its penetration through opened dentinal tubules to crystallize interlocking with dentin and provide mechanical properties. Biodentine has been developed using MTA based cement technology and hence; added improved properties such as physical qualities and handling, and its wide range of recommended applications in endodontic repair and pulp capping. [16]

Radiographic imaging of the dentoalveolar complex has been assessed using conventional periapical radiography, the benchmark for intraoral radiographic imaging for decades. Their known limitations of image magnification, distortion, superimposition and overlap of anatomy always led to unclear and misrepresentation of structures. Although the advent of digital intraoral radiography didn't improve these limitations, it provided a more active image manipulation than the film-based radiographs and reduced patient exposure

substantially. [17, 18]

7 - Objectives and hypothesis:

The objective of this prospective randomized clinical trial is to compare the clinical / radiographic outcomes of MTA and Biodentine as pulpotomy biomaterials used in apexogenesis treatment of symptomatic / asymptomatic vital immature mandibular permanent first molars with carious pulp exposure.

8-Trial Design:

Randomized clinical trial (RCT), parallel groups with 1:1 allocation ratio, Triple blinded (patient, clinical and radiographic assessor of the results and statistician)

III- Methods:

9-Study settings:

This study will be carried out on patients attending the outpatient clinic in Pediatric Dentistry department, Faculty of Dentistry, Cairo University, Egypt. the procedures will be carried out by [name] Associate Professor of Pediatric Dentistry in Pediatric Dentistry clinic. expected time duration from 2017 to 2018.

10- Eligibility criteria:

Inclusion criteria:

- Medically free children.
- Bilaterally Symptomatic / asymptomatic vital immature mandibular first permanent molars (with clinical carious exposure of the pulp and presence of bleeding upon exposure)
- Patients with an age range from 7-8 years.
- Absence of sinus tract, soft tissue swelling.

The exclusion criteria:

- Molars were excluded if non-restorable.
- excessive mobility (more than 1 mm horizontally).

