None needed.

12- Outcomes:

	Outcome	Tool/Device	Unit
Primary Outcome	spontaneous pain, sensitivity to percussion/ palpation)	Pain questionnaire	Binary
	Swelling or sinus tract	Visual examination by the third author	Binary
	Mobility	Back of the mirror	Binary
Secondary outcome	Stage of root development	Standardized periapical	3 stages
	Crown: Root ratio	Standardized periapical	2:1 ≥2:1
	Apex	Standardized periapical	Blunder apex, partially open, constricted
	Presence of radiolucency	Standardized periapical	Binary

Primary outcome:

Clinical assessment of the findings in the table will be conducted at follow up intervals (baseline, 6, 12 and 18 months)

Secondary outcome:

Radiographic assessment of stage of root development, crown: root ratio, apical closure and presence of radiolucency will be conducted through digital periapical radiographs by parallel

technique using film holders. The assessments will be carried out at follow up intervals (baseline, 6, 12 and 18 months)

13- Participants timeline:

	Study period				
	Enrolment	Allocation	Post allocation		Close out
Time point	For 7 months	0	6 months	12 months	18 months
Enrolment:					
Eligibility screen	✓				
Informed consent	✓				
History taking	✓				
Clinical examination	✓				
Preoperative radiograph	✓				
Allocation		✓			
Interventions:					
Access preparation		✓			
Placement of Biodentine (experimental group)		✓			
Placement of MTA (Control group)		✓			
Final restoration		✓			
Assessment					
Periapical radiograph as baseline reference			✓	✓	✓

Clinical examination to assess pain, swelling, fistula, tooth mobility			✓	✓	✓
Periapical radiograph to assess stage of root development, crown: root ratio, apical closure and presence of radiolucency			✓	✓	✓

14- Sample size calculation:

Sample size is calculated based upon the results of Alqaderi et al (2014) [15] who reported clinical success rate (primary outcome) for MTA = 90%. Since no relevant literature reported the clinical success rate of Biodentine in permanent teeth of pediatric patients, the success rate was assumed to be 50%. Using alpha level = 0.05 and β level = 0.20 (80% Power); the minimum estimated sample size will be 20 subjects per group for a total of 40 subjects. To compensate for a drop-out rate of 15%, the number is increased to 23 subjects per group for a total of 46 subjects.

Sample size calculation was performed using IBM® SPSS® Sample Power® Release 3.0.1.

15- Recruitment:

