All patients attending the outpatient clinic in pediatric dentistry department complaining from carious mandibular first permanent molars will be screened and enrolled in the study if they meet the eligibility criteria.

16- Allocation:

Sequence generation:

Access cavity prepared molars will be assigned into experimental or control group using simple randomization 1:1 by the help of the computer software(random.org).

Allocation concealment mechanism:

Numbered opaque sealed envelopes.

Implementation:

The child will choose an envelope randomly and open it after caries removal so that the operator knows which pulpotomy agent will be used only after finishing the access cavity. Sequence generation will be done by the third author and the patient assignment will be done by the operator.

17- Blinding:

Patients and their parents, the assessor and the statistician will be blinded.

18- Data collection methods:**Primary outcome:**

Clinical assessment of the following findings:

1. postoperative pain: through asking the child and the parent if there is pain either continuous or intermittent
2. Swelling: through visual examination by the assessor either intraorally or extra-orally.
3. Sinus or fistula through visual examination of the gingiva by the assessor.
4. Tooth mobility: By the back of the mirror checked by the assessor to detect mobility in any direction

This assessment will be conducted every follow-up visit throughout the study period at baseline, 6, 12 and 18 months.

Secondary outcome

Radiographic assessment to detect stage of root development, crown: root ratio, apical closure and presence of radiolucency through standardized periapical radiograph by parallel technique using film holder. This assessment will be conducted every follow-up visit throughout the study period at baseline, 6, 12 and 18 months.

Postoperative records will be performed by the assessor to avoid individual variability and to promote data quality.

19- Data management:

Explanation to the parents about the importance of the follow-up visits in addition to treatment of other dental problems are plans to promotes participants retention and complete the follow-up. Also, phone calls before the dates before the next follow-up visit will be scheduled.

All findings will be documented in the examination sheet then transferred electronically to computer in secured lace sequentially.

20- statistical methods:

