All data will be collected, checked, revised, tabulated and entered into the computer. Qualitative data will be presented as frequencies and percentages. Since the study is a split-

mouth design; Wilcoxon signed-rank test will be used to compare between the two groups. Friedman's test will be used to study the changes by time within each group. Kaplan-Meier survival curve will be constructed to calculate the mean survival estimates of the two groups. Comparison between survival times will be performed using Log rank test.

The significance level will be set at $P \leq 0.05$. Statistical analysis will be performed with IBM® SPSS® Statistics Version 20 for Windows.

21-Monitoring:

The study data and results will be monitored regularly by the assessor who will have full access to these data.

22- Harms:

No reported adverse effects for both testing pulpotomy agents. Any adverse events appear during the trial will be recorded, documented and treated.

23-Auditing:

Auditing of the study design will be done by the evidence-based committee, Faculty of Dentistry -Cairo University.

V- Ethics and dissemination:

24-Research ethics approval:

This protocol and the template informed consent form will be reviewed by the Ethics Committee of Scientific Research - Faculty of Oral and Dental Medicine - Cairo University.

25-Protocol amendments:

Any modification to the protocol which may have an impact on the conduction of the study, potential benefit of the patient or my affect patient safety including, the changes of study objectives, study design, sample size or significant administrative aspects will require a formal amendment to the protocol.

26-Consent and Assent:

Researcher will discuss the trial with legal guardian of each participating child. They will be able to have an informed discussion with the researcher after explaining the procedure in simple words. Verbal assent will be taken orally from the participating child while written consent will be taken from the legal guardian of each participating child who is willing to participate in the

® IBM Corporation, NY, USA.

® SPSS, Inc., an IBM Company.

trial. All consent forms will be translated into Arabic.

27-confidentiality:

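### The assessor is declared blinded, but the roles and data access set out in Sections 5, 12, 16, 21 and 29 do not protect that blinding

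*Combined protocol and SAP*

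**What the plan says.** **Blinding.** Section 8 describes the trial as "Triple blinded (patient, clinical and radiographic assessor of the results and statistician". Section 17 repeats it: "Patients and their parents, the assessor and the statistician will be blinded". Neither section says how the assessor is kept blind.

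**Sequence.** Section 16 states: "Sequence generation will be done by the third author and the patient assignment will be done by the operator". Concealment is by numbered, opaque, sealed envelopes. The child picks one at random and opens it once caries has been removed.

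**Outcome scoring.** In the Section 12 table the method for swelling and sinus tract is "Visual examination by the third author". Section 5 describes the third listed investigator as "Responsible for the clinical evaluation of the cases at the evaluation intervals". Section 18 has the assessor judge swelling, sinus or fistula, and mobility, and also make the postoperative records.

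**Monitoring and access.** Section 21 states: "The study data and results will be monitored regularly by the assessor who will have full access to these data". Section 5 describes the first listed investigator as "Responsible for the clinical part of study, and Data monitoring". Section 29 gives all principal investigators access to the data sets and masks information that would identify participants.

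**The concern.** The person who appears to score the clinical outcomes also produces the randomization list, and the assessor is given standing access to accumulating data and results. Both are ways in which a person declared blind could learn which material a molar received.

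The primary findings at stake are binary judgements made by eye and with a mirror handle. If the assessor knew the arm, borderline findings could be scored differently by arm. Visits scored with that knowledge could not be re-blinded afterwards, and the report could not defend its claim of a blinded assessor. Section 20 also calls the design split-mouth. If each child does receive both materials, learning the arm of one molar reveals the other.

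**Working it through.** No figure in the plan bears on this point, so the check sets the sections side by side.

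1. **Who is the assessor?** Sections 17, 18 and 21 say only that there is an assessor. Section 12 names the third author in 1 of 3 primary-outcome rows, and Section 5 gives the third listed investigator the clinical evaluation at follow-up. That the assessor is the third author is therefore an inference. It is a strong one for the clinical findings. It is weaker for the radiographs, whose reader is not clearly identified.

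2. **Does the list reveal the arm?** Not by itself. Because the child draws at random, knowing the order of the list does not say which envelope a given child opened. But the envelopes are numbered. Someone who holds the list and sees the number drawn knows the arm. The plan does not say whether that number is recorded, who can see it, or who prepares and holds the envelopes.

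3. **Do the monitored data reveal the arm?** Section 21 gives the assessor full access to data and results and makes no exception for allocation or for results by group. This step does not depend on the inference in step 1, since Section 21 names the assessor directly. Section 5 gives data monitoring to a different person, so the two sections disagree on who monitors.

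4. **Is there another route to the data?** Section 29 gives data-set access to all principal investigators without saying who they are. If the assessor is one of them, removing the monitoring duty from Section 21 would leave this access in place. The masking in Section 29 concerns participant identity, not the arm.

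5. **What protects the blinding?** Section 17 states a general rule. Section 16 has opaque envelopes drawn at random, and assignment is done by the operator, not by the person who made the list. Section IV gives both arms the same glass ionomer restoration over the agent, so it describes no visible difference in the final restoration. None of these closes the routes in steps 2 to 4.

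6. **How much of the primary outcome is exposed?** Section 18 names the assessor for 3 of 4 listed clinical findings. This shows where the assessor examines, not where the arm is known.

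**The case against.** The strongest reply is that Section 17 is itself a rule. Read with it, the access in Section 21 could mean outcome data stripped of allocation. If Section 5 governs monitoring instead, the Section 21 route disappears. The list route needs a recorded link between child and envelope number that the plan never describes, and identical restorations make a blinded clinical examination feasible.

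Much of this stands. A reader might infer that the assessor will know the arms, or that the triple-blind description is false. The documents do not support that: no passage gives the assessor the arm of any molar, and Section 17 says the opposite. A reader might also infer from the child opening the envelope that patients are unblinded. The envelope's content is not described, so this is wording to clarify and not evidence of unblinding.

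What the reply does not do is supply a mechanism. A declaration of blinding gives the team nothing to follow when other sections assign the assessor tasks that could undo it. Making Section 5 govern does not settle the matter either. If the first author monitors, and is the operator as the clinical role in Section 5 suggests, then the monitor knows the material used, and Section 29 access remains open.

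**Conclusion.** The point holds as a conflict between a declared property and the roles assigned around it: assessor blinding is claimed but not protected. It should be fixed, because the repair is cheap and it guards the scoring of the primary outcome. It does not show that blinding has failed or will fail.

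No size of bias can be given from the documents. The risk is confined to a recorded envelope number the assessor can see, or to data that carry the arm or show results by group. The conclusion about the list rests on the inference that the third author is the assessor. The conclusion about Section 21 does not. The conclusion about Section 29 depends on whether the assessor counts as a principal investigator. The case is firmest for the clinical outcomes.

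**What to change.** 1. **Section 16.** Have someone who neither operates nor assesses generate and hold the list and prepare the envelopes. The second author is one candidate, if available, since Section 5 describes that author as "responsible for the writing revision and proof reading". Keep the rule that the envelope is opened only after the access cavity is finished.

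2. **Sections 5, 21 and 29.** Name one monitor consistently, and take the assessor off monitoring of accumulating data and results. Code the arms A/B in the data set. Until all assessments are complete, give the assessor only visit forms without material, envelope number or results by group, and state that this limit also applies to access under Section 29. If the first author monitors, state that this person (read here as the operator) is unblinded and does not score outcomes.

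3. **Sections 16 and 17, minor wording.** Reconcile the child opening the envelope with the child being blinded, for example by saying how its content is kept from the child and parents.

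The cost is a small reassignment of tasks and edits to these five sections, with no extra patients or visits. The downside is that if the first author keeps monitoring, an unblinded monitor who reviews results of procedures that he or she performed must be declared.

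### Percussion/palpation sensitivity is in the primary outcome, but no test for it is specified, and pain is not stated to be recorded by tooth or side

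*Combined protocol and SAP*

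**What the plan says.** The outcomes table, given in Section 6 and again in Section 12, opens the primary outcome with "spontaneous pain, sensitivity to percussion/ palpation". It is binary, and its only tool is "Pain questionnaire". The other primary rows each name an examination: visual inspection for swelling or sinus tract, and the back of the mirror for mobility. Below the table, Section 12 adds: "Clinical assessment of the findings in the table will be conducted at follow up intervals".

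The Section 13 timeline describes the clinical visit as "Clinical examination to assess pain, swelling, fistula, tooth mobility".

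Section 18 lists four primary findings: pain, swelling, sinus or fistula, and mobility. Pain is obtained "through asking the child and the parent if there is pain either continuous or intermittent". Mobility, by contrast, has a tooth-level method: "By the back of the mirror checked by the assessor to detect mobility in any direction".

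On the unit of study, Section 10 requires "Bilaterally Symptomatic / asymptomatic vital immature mandibular first permanent molars", and Section 16 allocates molars. Section 8 describes parallel groups, while Section 20 calls the design split-mouth and plans a paired test.

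**The concern.** There are two linked gaps.

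First, percussion or palpation sensitivity is the response when an examiner taps or presses, so it has to be elicited at the chair. The tool listed for it cannot do that, and the two sections that put the outcome into operation do not mention it. An examination sheet built from Section 18 would have no field for it. Teeth that fail on this component alone would be counted as successes, which raises the reported success rate in both arms and narrows any difference between them.

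Second, the pain item has no stated tooth or side. Every eligible child has disease in both mandibular first molars, and the respondents are children aged 7 to 8 and their parents. If both molars are study teeth with different materials, pain with no side attached must either be scored on both, which turns an informative pair into a tie, or be assigned by guess. Percussion and palpation are findings that could help tie a symptom to one molar, and they are the ones without a method.

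**Working it through.** **Setting the sections side by side**

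| Component | Section 12 tool | Section 13 timeline | Section 18 list |
|---|---|---|---|
| Pain | Questionnaire | Listed | Ask child and parent; side not stated |
| Percussion/palpation sensitivity | Questionnaire | Not listed | Not listed |
| Swelling, sinus tract | Visual examination | Listed | Visual examination |
| Mobility | Back of the mirror | Listed | Back of the mirror |

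Only the second row has no workable method anywhere.

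**Reproducing the plan's sample size**

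Inputs from Section 14: success 90% (MTA) and 50% (Biodentine), alpha 0.05 (taken as two-sided), power 80%. With the pooled two-proportion formula and mean proportion 0.70:

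n = [1.96 × √(2 × 0.70 × 0.30) + 0.842 × √(0.90 × 0.10 + 0.50 × 0.50)]² / 0.40² = 19.4, so 20 per group.

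This matches the plan. Power at 20 per group is 81.3%.

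**Illustration A: failures that show only on percussion/palpation are missed**

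Assume a share s of failures in each arm shows only on this component. The recorded failure rates become 0.10(1 − s) and 0.50(1 − s), so the difference becomes 0.40(1 − s). Power = Φ{[difference × √n − 1.96 × √(2p̄(1 − p̄))] / √(p₁(1 − p₁) + p₂(1 − p₂))}, where p₁ and p₂ are the recorded success rates and p̄ is their mean.

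| s | Recorded success | Difference (points) | Power, 20 per group | Power, 23 per group |
|---|---|---|---|---|
| 0 | 90% vs 50% | 40 | 81% | 87% |
| 0.1 | 91% vs 55% | 36 | 75% | 81% |
| 0.2 | 92% vs 60% | 32 | 67% | 73% |
| 0.3 | 93% vs 65% | 28 | 59% | 65% |

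The 23 per group is the plan's enrolled number, and that column assumes no dropout.

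**Illustration B: split-mouth reading, unlocalised pain scored on both molars**

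Assume one molar per material in each child, with independent sides. The discordant probabilities are 0.50 × 0.90 = 0.45 (Biodentine fails alone) and 0.10 × 0.50 = 0.05 (MTA fails alone). If a share s of one-sided failures is pain-only and scored on both molars, those pairs become ties, leaving 0.45(1 − s) and 0.05(1 − s). Power is for the uncorrected McNemar test at two-sided 0.05, by full enumeration.

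| s | 20 pairs | 46 pairs |
|---|---|---|
| 0 | 79% | 99% |
| 0.25 | 65% | 96% |
| 0.5 | 47% | 84% |

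Both columns are needed because the documents do not state the number of pairs: 20 pairs is the low reading of Section 14, and 46 pairs takes its total as children with two study molars each. An exact sign test on 23 pairs gives 78%, 59% and 29% for the same three shares.

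**The case against.** A reader might infer that percussion sensitivity is never measured. The documents do not support that. Section 12 commits to clinical assessment of the findings in its table, and the timeline includes a clinical examination for pain, so an assessor could test percussion under that general statement. What stands is narrower: no method is specified, and the sections disagree.

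A reader might also infer that pain is asked once per child and so cannot be assigned to a molar. The text says neither. It does not state the unit of the question, the examination sheet is not reproduced, and recording by tooth is not ruled out. What stands is that no provision for tooth or side is stated, nor any rule for pain that cannot be localised.

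Nor is it clear that Section 18 replaces spontaneous pain with something else. Continuous or intermittent describes the time pattern and is compatible with spontaneous pain. The wording is loose and should be aligned, no more.

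The tied-pair argument needs the split-mouth statement in Section 20, which conflicts with Section 8 and with the subjects per group in Section 14. With one study molar per child there are no pairs to tie, although bilateral disease can still blur the source of pain. Even with two study molars per child, the simple randomization of molars in Section 16 does not guarantee that they receive different materials.

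Finally, the illustrations lean pessimistic. Every share is assumed. Illustration A lets no percussion-only failure show up later through another sign, and B scores every pain-only one-sided failure on both molars.

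**Conclusion.** The point holds as an inconsistency in the primary outcome. A component named in Section 12 has an unsuitable tool and is absent from Sections 13 and 18, so following Section 18 as written gives a primary outcome different from the one defined. This is so under either design. The lack of a stated tooth or side for pain is a second gap, with full force only if the trial is split-mouth.

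The size is conditional, because the documents give no split of failure types. For missed percussion-only failures at assumed shares of 10% to 30%, the loss is about 7 to 22 percentage points of power at 20 per group. For tied pairs at assumed shares of 25% to 50%, it runs from 14 to 32 points with 20 pairs, but only 3 to 15 with 46 pairs. These figures show direction and plausible range; they do not estimate the actual loss. The change should be made before data collection, since an unrecorded percussion response or pain side cannot be reliably recovered afterwards.

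**What to change.** - **Sections 12, 13 and 18:** make the list of primary components identical. Have the assessor, blinded under Section 17, record sensitivity to percussion and to palpation as yes/no for each study molar at the scheduled visits. List examination, not questionnaire, as the tool. Removing the component from the outcome would also end the contradiction, but would give up a tooth-level finding.
- **Pain item:** use the term spontaneous pain throughout, record it by side, and state in advance how pain that the child cannot localise is scored.
- **Primary outcome:** state that it is built from these per-molar records.
- **Design:** reconcile Sections 8 and 20, since the consequence of unlocalised pain depends on whether children contribute one molar or two.

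The cost is some rewording, a few more fields on the examination sheet and slightly longer examinations. No extra visit, staff or equipment is needed, because the assessor already examines each molar for mobility.

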- Radiographic evidence of peri- and /or inter-radicular lesions, internal/ external root resorption, pulp/ canal calcifications.

IV- Intervention:

Diagnosis:

1. Full history data will be collected, including personal, medical and previous dental data
2. Clinical examination using mirror and probe to assess the inclusion criteria.
3. Radiographic examination using preoperative digital periapical radiograph to assess the inclusion criteria.
4. Preoperative photograph will be taken.

Operative procedure:

Experimental group:

1. Injection of local anesthesia and rubber dam isolation.
2. caries and roof of the pulp chamber will be removed by a fissure diamond bur (Diatech, Heerbrug, Switzerland) and high-speed handpiece with coolant.
3. The pulps will be amputated to the orifice level using a long-shank diamond round bur.
4. Haemostasis will be achieved by gentle placement of a saline-moistened cotton pellet over amputated pulps for 5–10 min.
5. Calcium silicate-based BiodentineTM (Septodont Ltd., Saint Maur des Fausse's, France) will be mixed according to the manufacturer's instructions, radicular pulp will be covered by the material using a wet cotton pellet.
6. A self-cure glass ionomer (GC; GC Corporation, Tokyo, Japan) will be placed over the pulpotomy agent as a final restoration.
7. Immediate post-operative radiograph and photograph will be taken.

Control group:

The same procedures will be carried out as the experimental group, but the pulp stumps will be covered with fast-setting mineral trioxide aggregate (MTA) ENDOCEM MTA (Maruchi, Wonju, Korea) and will be prepared according to the manufacturer's instructions. A 3-mm-thick layer of MTA will be placed over the amputated pulps and will be gently adapted to the dentinal walls using a wet cotton pellet. A self-cure glass ionomer (GC; GC Corporation, Tokyo, Japan) will be placed over the pulpotomy agent as a final restoration.

Postoperative care:

Instructions to avoid lip and cheek biting in addition to oral hygiene measures.

Follow up:

Assess the outcomes clinically and radiographically at (baseline, 6, 12 and 18 months).

Criteria for discontinuing or modifying intervention:

In case of an unsuccessful outcome after pulpotomy, the molars will be managed by other pulp therapy techniques or extraction.

Strategies to improve adherence to intervention:

Explanation to the parents about the importance of follow up visits in addition to treatment of other dental problems.

Concomitant care:

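### The radiographic assessor is declared blind, but the plan describes no safeguard for reading postoperative films that include the chamber holding the allocated material

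*Combined protocol and SAP*

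**What the plan says.** **The blind.** Section 8 describes the trial as "Triple blinded (patient, clinical and radiographic assessor of the results and statistician". Section 17 repeats the claim: "Patients and their parents, the assessor and the statistician will be blinded". Neither section says how the blind is kept when films are read.

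**The outcomes.** Section 18 sets out the secondary outcomes as "Radiographic assessment to detect stage of root development, crown: root ratio, apical closure and presence of radiolucency through standardized periapical radiograph". Section 12 says the radiographs are digital. Section 18 also states: "Postoperative records will be performed by the assessor to avoid individual variability and to promote data quality".

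**The materials.** In part IV, step 5 for the experimental group says of Biodentine that the "radicular pulp will be covered by the material using a wet cotton pellet", with no thickness. The control group text says: "A 3-mm-thick layer of MTA will be placed over the amputated pulps". In both arms a self-cure glass ionomer "will be placed over the pulpotomy agent as a final restoration".

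**The concern.** A blind for an image reader has two parts. The reader must not be told the arm, and the image must not show it. The plan asserts the first and does not address the second. The pulpotomy agent stays in the tooth, within the field of the films from which the secondary outcomes are read.

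The research question is half radiographic, and these readings are the only evidence for that half. Root stage and apex each have three ordered categories, and radiolucency is present or absent. Such calls have borderline cases, and a reader who knows or guesses the material may resolve them differently by arm. If one assessor reads all visits, a cue learned once carries through the series.

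**Working it through.** The plan gives no figure on this point, and its sample-size calculation (Section 14) concerns the clinical outcome and does not bear on it. The check is a comparison of sections.

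1. **Is a blind promised for the film readings?** Yes. Section 8 names the radiographic assessor explicitly, and Section 17 includes the assessor.

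2. **Does the allocated material lie in the imaged field?** Yes. Part IV has the pulp removed down to the orifices and the agent placed on the stumps, so it sits in the chamber. Crown:root ratio, one of the four outcomes, needs the crown in view. Films that can serve all four outcomes therefore include the chamber.

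3. **Is there a possible cue?** Two different products are used. A layer of 3 mm is stated for MTA, and none is stated for Biodentine. The overlying restoration is the same in both arms and gives no cue. Whether the agents or their layers look different on film is not stated anywhere.

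4. **Is a safeguard described?** None was found in Sections 12, 17, 18 or 19: no image coding, masking, reading order, second reader or check of the blind. The coded ID in Section 27 protects participants' identity on study forms. It is not described as a means of hiding the arm on images.

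5. **Which readings are exposed?** Films taken after placement: those at 6, 12 and 18 months, and the immediate postoperative film if it serves as baseline, which the plan leaves open. The preoperative film is not exposed.

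6. **Does the design matter?** Section 8 says parallel groups. Section 20 says split-mouth, and Section 10 asks for bilateral molars. Under split-mouth, each child would show both materials, and recognising one would reveal the other. Under parallel groups, that side-by-side comparison is absent.

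7. **What can be quantified?** The bias would depend on how often the reader identifies the material and how far that shifts borderline calls. The documents give neither quantity, so no estimate follows.

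**The case against.** The strongest reply is that the deciding premise is missing from the documents. Seeing a material reveals the arm only if the two can be told apart. No section gives radiopacity, density or appearance for either product, and the background describes Biodentine as built on MTA-type cement technology, which does not suggest a visible contrast. This stands, and it makes the conclusion conditional.

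Three stronger readings are tempting and are not supported:

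- **That the films will be read unmasked.** The plan is silent on masking, and silence does not establish that none is used.
- **That the plan itself makes the two layers differ.** A thickness that is not stated is not a different thickness. The control text also opens by carrying over the experimental procedures. What exists is a gap in wording between the arms.
- **That the number of postoperative films measures the problem.** That number changes with the parallel or split-mouth reading and with dropout, and it says nothing about bias.

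It is also fair to say that the affected outcomes are all secondary, that crown:root ratio is less open to judgement than the other three, and that a mask near the orifices could intrude on the cervical line or furcation. Radiolucency has no defined site in the plan, so a mask could hide part of what is scored. These points limit how the remedy is designed. They do not remove the need for one, because keeping the allocation list from the reader leaves the image itself unprotected.

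**Conclusion.** The concern holds in conditional form. The plan promises a blind for the radiographic reader and describes nothing to protect it on postoperative films that include the allocated material. If the materials can be distinguished, by appearance or by layer, the blind fails for those secondary readings, with most at stake for root stage, apex category and radiolucency. If they cannot, the safeguard costs little. The size of any bias cannot be derived, and the documents do not show that the blind does fail. This is an improvement the sponsor should make. It leaves the primary clinical outcome untouched.

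A separate problem remains. Section 16 states "Sequence generation will be done by the third author", while Sections 5 and 12 give clinical evaluation to the same author, and Section 21 gives the assessor full access to the data. If that person also reads the films, which the documents do not state outright, masking would not restore the blind. Conversely, reassigning sequence generation would not remove a cue on the film.

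**What to change.** In Sections 17 and 18, state that:

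- existing staff other than the assessor export the digital films under the coded ID, with no mark of the arm;
- they cover the restoration and chamber contents by one fixed rule, the same in both arms, that leaves the crown outline, cervical line, furcation, roots and apices visible;
- the copies are presented in random order, and the assessor scores only these copies;
- where the mask would obscure a listed outcome, that outcome is scored from the coded, randomly ordered film without the mask, and this is reported.

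The rule must be fixed in advance because whoever applies it may know the arm. Section 17 should also say who reads the films. The layer-thickness wording for the two arms in part IV should be reconciled; this review does not suggest a thickness.

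The cost is a few minutes of editing per film by existing staff, with no extra visit, exposure or participant. Chamber-level findings are hidden on the masked copy; the unmasked original can be kept on file.
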